4.2 Subject Exclusion Criteria

Subjects must **not meet any** of the following exclusion criteria at the time of the audit to be included:

- Subject under treatment at the study site's outpatient clinics;
- Subject admitted into a mental health ward, emergency ward or burn unit;
- Subject awaiting transfer to another facility.

4.3 Subject Informed Consent

The Investigator at each site must obtain a written informed consent of all subjects to participate in the study, before study-related procedures. Full and adequate information about the nature, purpose, possible risks and benefits of the study must be provided. Subjects must also be notified that they are free to discontinue their participation in the study at any time. The subjects should be given the opportunity to ask questions and allowed time to consider the information provided.

As delineated in [ResolutionNo466](#) and [PANDRH-GCPs](#), the ICF content should be briefly and clearly presented orally, and in writing, in a manner that is easy to understand, commensurate with the comprehension level of the research participants, and without coercion or unduly influencing a potential participant to enroll in the study. Specifically, the Investigator is to explain to each subject all elements of informed consent as specified in ANVISA Regulatory Guidelines.

After the explanation, the subject or representative will voluntarily sign and date the consent form if they wish to participate in the study. An original version of the consent form must be provided to the subject. Another original signed and dated version of the ICF must be

maintained in the Investigator study documentation file at all times. The process of consent and study participation, with date, must be documented in the patient record/chart.

4.3.1 Confidentiality of study/subject data

The Subject ICF will incorporate wording that complies with relevant data protection and privacy legislation. Pursuant to this wording, subjects will authorize the collection, use and disclosure of their personal data by the Investigator and by those persons who need that information for the purposes of the study.

The Subject ICF will explain that study data will be stored in a computer database, maintaining confidentiality in accordance with the local law for Data Protection. The subject should be informed that all data will be anonymized and grouped for analysis, making it impossible to identify unique patient data.

The Subject ICF will also explain that, for quality check purposes, a monitor of 3M or designee, will require direct access to the signed subject ICFs and to the source documents that are part of the hospital or practice records relevant to the study.

5. Assessment of Safety

5.1 Adverse Events Definitions

An adverse event is any undesirable clinical occurrence, whether it is considered to be device- or drug-related or not.

5.2 Anticipated Device-Related Adverse Events

This is an observational, cross-sectional study that is not designed to identify or quantify a safety hazard relating to an authorized medicinal product or medical device. Nevertheless, there are anticipated device-related adverse events that may occur during this study and are related to the current practice of PIVC therapy at the study sites. According to IV professionals and IV-related literature, the anticipated device-related adverse events that may occur are:

1. Certain skin reactions, such as mild to moderate redness, blisters, itching, and/or minor skin denudations at the site of the adhesive which should dissipate within one to seven days after removal;
2. Loss of the PIVC from the insertion site;
3. Leaking of fluid or blood from PIVC insertion site;
4. Phlebitis and/or;
5. Infiltration of an infusate.

5.3 Unanticipated/Serious Device Related Adverse Events:

The following list of unanticipated and/or more serious device-related adverse events are unlikely to be identified during this study, unless the audit nurse reads of the event during the medical record review. Excluding the severe skin reactions, the nurse auditors will most likely not be aware of the following unanticipated and/or serious adverse events:

1. Any catheter-related phlebitis with a fever;
2. A catheter-related phlebitis or infiltration that extends hospitalization;
3. A catheter-related blood stream infection (PIV-CRBSI);
4. Severe skin stripping or skin reaction; or
5. Extravasation.

5.4 Recording and Reporting Adverse Events

PIVC-related adverse events can occur at any time during the conduct of the study and may be identified by the Investigator (or designee), auditor or patient. The auditor who observes a PIVC-related adverse event or is told of an adverse event by the patient is responsible for reporting the event to the nurse caring for the patient. The patient's nurse and/or physician will be responsible for treating the patient. The country's and/or hospital's formal adverse event (incident) reporting process will be used to document the adverse event.

If the PIVC-related adverse event is also a PIVC-related complication of interest for the study (Section 3.3), their presence will be documented by study personnel in the corresponding Individual PIVC Questionnaire. There is no requirement for any additional information on adverse events to be recorded in the eCRF. Further details on adverse events that are also complications of interest for the study will be processed in accordance with the abovementioned country's or hospital's formal adverse event (incident) reporting process.

6. Statistics

6.1 Study endpoints

- 6.1.1 Primary endpoint
- Proportion of PIVCs sites with at least one clinical or mechanical complication.
- 6.1.2 Secondary endpoints
- Proportion of PIVC sites with at least one clinical and one mechanical complication.
- Proportion of PIVC sites with at least one clinical complication and with each specific clinical complication.
- Proportion of PIVC sites with at least one mechanical complication and with each specific mechanical complication.
- Proportion of PIVC sites with at least one related quality issue and with each specific quality issue.
- Frequency distribution for the PIVC Standards of Practice.

6.1.3 Exploratory endpoints

Measures of association between PIVC-related complications and sociodemographic characteristics, as well as between PIVC-related complications and other baseline characteristics will be examined, if appropriate.

6.2 Statistical Methods

6.2.1 General aspects

For the purposes of the present study, the unit of analysis will be the individual PIVC sites and not the patients in which they are inserted.

Descriptive statistics will be obtained for numerical variables, including central tendency measures such as mean, median as well as the dispersion measures of standard deviation, min-max and inter-quartile range. Descriptive statistics for categorical variables will include frequencies' tabulation with counts and percentages. No imputation of missing values will be made. 95% confidence intervals will be used if applicable. The significance tests of association under exploratory analyses will be made at the 5% significance level.

Data will be presented for the overall study sample, as well by hospital and by hospital ward.

6.2.2 Primary endpoint analysis

The prevalence of PIVC-related complications among the PIVC sites audited at the participating acute care hospitals in Brazil will be determined as follows:

- Prevalence (%) = (Number of audited PIVC sites with at least one clinical or mechanical complication ÷ Number of audited PIVC sites) x 100

The definitions of clinical and mechanical complications are detailed in Section 3.3 and Appendix I.

6.2.3 Secondary endpoint analyses

- The prevalence of PIVC-related clinical and mechanical complications among the PIVC sites audited at the participating acute care hospitals in Brazil will be determined as follows:
 - Prevalence (%) = (Number of audited PIVC sites with at least one clinical and one mechanical complication ÷ Number of audited PIVC sites) x 100
- The prevalence of PIVC-related clinical complications among the PIVC sites audited at the participating acute care hospitals in Brazil will be determined as follows:
 - Prevalence (%) = (Number of audited PIVC sites with at least one clinical complication ÷ Number of audited PIVC sites) x 100
 - Prevalence (%) = (Number of audited PIVC sites with each specific clinical complication ÷ Number of audited PIVC sites) x 100
- The prevalence of PIVC-related mechanical complications among the PIVC sites audited at the participating acute care hospitals in Brazil will be determined as follows:
 - Prevalence (%) = (Number of audited PIVC sites with at least one mechanical complication ÷ Number of audited PIVC sites) x 100
 - Prevalence (%) = (Number of audited PIVC sites with each specific mechanical complication ÷ Number of audited PIVC sites) x 100
- The prevalence of PIVC-related quality issues among the PIVC sites audited at the participating acute care hospitals in Brazil will be determined as follows:
 - Prevalence (%) = (Number of audited PIVC sites with at least one quality issue ÷ Number of audited PIVC sites) x 100
 - Prevalence (%) = (Number of audited PIVC sites with each specific quality issue ÷ Number of audited PIVC sites) x 100

The definitions of clinical and mechanical complications, as well as of quality issues, are detailed in Section 3.3 and Appendix I.

PIVC Standards of Practice will be summarized using descriptive statistics.

6.2.4 Exploratory endpoint analyses

Exploratory analyses will be performed with the aim of identifying the subject- and PIVC characteristics associated with the occurrence of PIVC-related complications.

The association of qualitative variables with the occurrence of PIVC-related complications will be performed with the chi-squared test or with the Fisher's test, while the association of quantitative variables with the occurrence of PIVC-related complications will be performed with the student's t test or the Mann-Whitney test.

Generalized estimating equation (GEEs) models will be used to identify the most important patient characteristics associated with the multivariate binary occurrence of PIVC-related complications, with a Logit link function and considering the correlation structure assumed as exchangeable within patients. The Odds Ratios as well as 95% confidence intervals will be estimated. The significance level will be established at 5%.

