 - According to etiology: mechanical, chemical, infective
 - Hematoma
 - Ecchymosis
 - Skin injury
 - Local infection
- Mechanical complications:
 - Catheter dislodgement
 - Occlusion
 - Extravasation
 - Infiltration (grade 1-4)
 - Leaking at the insertion site

The PIVC will also be evaluated for the presence of the following quality issues:

- Unstable PIVC
- Blood reflux
- Uncontrolled IV infusion rate
- Site dressing partially detached
- Site dressing totally detached (site exposed to environment)

- Medical tape added to dressing edges
- Unclean dressing
- Discomfort at site with or without palpation
- Uncovered tubing access port
- Lack of visibility at the PIVC site

If the patient has more than one PIVC, one questionnaire will be completed for each PIVC.

Once the wards' audits are concluded, the study-specific electronic case report forms (eCRFs) will be completed by the PI or study designee. The sponsor or sponsor's representative will perform the monitoring activities and, based on the number or type of inconsistencies/ queries raised, the monitor may deem that the site requires additional training. Once the additional training is complete, the audit process will continue with any changes deemed necessary by the monitor to improve the quality and quantity of data collected.

The process of PIVC-related data collection will be repeated at each study site until at least 100 PIVCs have been audited (Table 1).

Table 1 - Study data collection and procedures per audited ward

Study procedures ^a	Pre-audit	Audit day
Completion of hospital's or ward's current PIVC Therapy Standards of Practice Questionnaire ^b	X	
Inclusion and exclusion criteria review		X
Informed consent form signature		X
Completion of Individual PIVC Questionnaires		X

a. Procedures and timeline to be repeated if more than one ward is to be audited at the study site.

b. Repeat survey of current PIVC standards of practice, if the standards are ward-specific.

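### The univariable tests in section 6.2.4 treat PIVCs as independent, although one patient may contribute several and the GEE in the same section assumes they are correlated

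*Combined protocol and SAP*

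**What the plan says.** Section 6.2.1 fixes the unit: "the unit of analysis will be the individual PIVC sites and not the patients in which they are inserted". Section 3.3 allows repeated units from one person: "If the patient has more than one PIVC, one questionnaire will be completed for each PIVC". Section 4.1 sets a minimum of one catheter per patient and no maximum.

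The exploratory work in section 6.2.4 is to be done "with the aim of identifying the subject- and PIVC characteristics associated with the occurrence of PIVC-related complications". It has two parts:

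- **Univariable tests.** "The association of qualitative variables with the occurrence of PIVC-related complications will be performed with the chi-squared test" or Fisher's test. Quantitative variables get a t test or a Mann-Whitney test. No allowance for clustering is stated.
- **GEE models.** These are planned "to identify the most important patient characteristics associated with the multivariate binary occurrence of PIVC-related complications", with a logit link and "considering the correlation structure assumed as exchangeable within patients".

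On intervals, section 6.2.1 says only: "95% confidence intervals will be used if applicable". It adds: "Data will be presented for the overall study sample, as well by hospital and by hospital ward". Sections 6.2.2 and 6.2.3 give prevalence formulas without an interval.

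**The concern.** Two catheters in one patient share that patient's veins, drugs, nursing and skin, so their outcomes are likely to be correlated. The GEE specification accepts this, while the four univariable tests in the same section ignore it. For a factor that is constant within a patient, such as age or gender, a test that counts each PIVC as a separate piece of evidence rejects too often. A univariable p-value and a GEE p-value for the same factor could then disagree only because one of them ignores the pairing.

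The GEE may also not cover every factor of interest. The section's aim names subject and PIVC characteristics, but its GEE sentence names patient characteristics only. Section 3.4.1 lists date of birth, initials and gender as the socio-demographic variables, against a long list of PIVC variables. Read literally, the PIVC variables would get only the unadjusted tests.

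**Working it through.** **The plan's own figure.** Section 6.3 gives 100 PIVCs per hospital and 300 in total; 3 x 100 = 300 agrees. Section 6.3 states that no formal calculation was made, so there is no power or precision figure to reproduce.

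**Inputs.**

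- From the documents: n = 300 (section 6.3) and the 5% level (section 6.2.1), taken as two-sided.
- Assumed, because the documents are silent: the share f of patients with two PIVCs (0.1, 0.2, 0.4; the rest have one), and the within-patient intraclass correlation (ICC) on the observed binary scale (0.2, 0.5, 0.7).
- Assumed, for the half-widths only: prevalence p = 0.35.

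**Formulas.** The size-weighted mean number of PIVCs per patient is m = (1 + 3f)/(1 + f). For a factor whose own correlation within patients is c, the approximate design effect is DE = 1 + (m - 1) x ICC x c. The true size of an unadjusted nominal 5% test is 2 x [1 - Phi(1.96/sqrt(DE))].

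- c = 1: constant within a patient (age, gender).
- c = 0: varies freely between a patient's PIVCs. DE = 1, so the size stays at 5%.
- c = -1: always differs between a patient's two PIVCs.

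**Results.**

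| f | ICC | DE, c = 1 | Size, c = 1 | DE, c = -1 | Size, c = -1 |
|---|---|---|---|---|---|
| 0.1 | 0.2 | 1.036 | 5.4% | 0.964 | 4.6% |
| 0.1 | 0.7 | 1.127 | 6.5% | 0.873 | 3.6% |
| 0.2 | 0.2 | 1.067 | 5.8% | 0.933 | 4.2% |
| 0.2 | 0.5 | 1.167 | 7.0% | 0.833 | 3.2% |
| 0.2 | 0.7 | 1.233 | 7.8% | 0.767 | 2.5% |
| 0.4 | 0.2 | 1.114 | 6.3% | 0.886 | 3.7% |
| 0.4 | 0.7 | 1.400 | 9.8% | 0.600 | 1.1% |

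One row in full: f = 0.4 gives m = 2.2/1.4 = 1.571. With ICC = 0.7, DE = 1 + 0.571 x 0.7 = 1.400 and 1.96/sqrt(1.400) = 1.656, so the size is 9.8%.

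**Simulation check** (300 PIVCs, same ranges of f and ICC).

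- Patient-level factor: chi-squared 5.4%-9.6%, t test 5.2%-9.6%, Mann-Whitney 4.6%-10.7% (fewer replicates).
- Freely varying PIVC factor: 4.6%-5.3%.
- PIVC factor shared by a patient's two PIVCs half the time: 4.8%-7.0%.
- Factor that always differs: 1.5%-4.4%, close to the formula's 1.1%-4.6%.

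**Prevalence interval.** The half-width is 1.96 x sqrt(p(1 - p) x DE/300). With DE = 1 it is 1.96 x sqrt(0.35 x 0.65/300) = 5.4 points. With DE = 1.036 it is 5.5 points, and with DE = 1.400 it is 6.4. Ignoring the pairing would therefore understate the half-width by about 0.1-1.0 points. The corresponding effective sample sizes run from 300/1.036 = 290 down to 300/1.400 = 214.

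**Check of the remedies.** In simulation, single-covariate logistic GEE, exchangeable within patient, had size 3.9%-4.7% for a binary patient-level factor and 4.6%-5.0% for a continuous one. A patient-robust Wald interval for the overall prevalence covered 94.8%-95.0%. It fails in small groups. With 10 PIVCs in a ward it covered 84%-87%, against 92%-96% for a plain Wilson interval. For a 5% complication in 100 PIVCs it covered 84%-87%, against 93%-97%.

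**The case against.** The strongest reply is that the gap and the harm hardly overlap. The clear inflation is for age and gender, and the planned GEE already handles those with within-patient correlation. PIVC factors, for which the GEE wording is doubtful, are tested near 5% if they vary freely and conservatively if they differ within patients. The top of the range needs 40% of patients with two PIVCs and a high correlation, and the low end is almost no effect. Section 6.1.3 makes these analyses exploratory, to be done where appropriate. All of this stands and limits the severity. It does not make the four tests right for these data, and correcting them costs little.

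Four stronger readings are tempting, and the documents do not support them:

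- **That the GEE definitely excludes PIVC characteristics.** This is the literal reading of one sentence. The section's opening aim includes them, and a model limited to age and gender would be nearly empty, so the word patient may be loose drafting.
- **That the unadjusted tests always reject too often.** The direction depends on how the factor varies within a patient.
- **That the plan specifies a wrong confidence interval.** It names no method. That is a gap.
- **That ward clustering makes the prevalence intervals far too narrow.** That follows only if the wards are treated as random draws from a wider population. Sections 6.2.2 and 6.2.3 word the target as the audited sites. With the audited wards taken as fixed, and patient pairing left aside, a binomial interval covered 94.9%-96.0% in simulation. Section 2.1 words the target more widely, but that is a question of what the estimate refers to and does not by itself show an error in the interval.

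**Conclusion.** The point holds, and it is minor. Section 6.2.4 applies four independence-based tests to units that the plan itself treats as correlated a paragraph later. For age and gender the true size of a nominal 5% test is about 5.4%-9.8%, if 10-40% of patients have two PIVCs and the observed-scale ICC is 0.2-0.7. For PIVC factors it is about 5% if they vary freely, and roughly 1%-5% if they always differ within patients. These ranges rest wholly on assumed inputs. No confirmatory error rate is at stake, and the crude prevalence estimates are unaffected.

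**What to change.** **Section 6.2.4, univariable analyses.** Replace the four tests with single-covariate GEE (logit link, exchangeable within patient, robust standard errors) or Rao-Scott tests clustered on patient, for both subject and PIVC characteristics. Quantitative variables enter as the covariate. Where a table is too sparse for GEE, collapse categories or use Fisher's test on one randomly chosen PIVC per patient.

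**Section 6.2.4, multivariable GEE.** Word it to include PIVC characteristics, in line with the section's stated aim.

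**Sections 6.2.1 to 6.2.3, intervals.** Name the method. For the overall and other well-populated prevalences, use an interval that allows for patient clustering, for example a Wilson interval with n divided by the estimated design effect. For ward-level estimates and rare complication types, use a Wilson or exact interval and state that clustering is not covered, because a patient-robust Wald interval under-covers there.

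A ward-clustered sensitivity analysis and a hospital fixed effect are not required by this point.

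**Cost.** SAP wording and slightly more code. No new data are needed, since the planned GEE already requires the link from PIVC to patient. Overall intervals widen by about 0.1-1.0 points on the half-width under the assumed inputs. The single-covariate GEE was checked on one binary and one continuous factor only, so sparse multi-level factors such as gauge or dressing type will need the fallback stated above.

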1.3 Investigational Material Application

No investigational materials will be provided or used in this prevalence study. All PIVC-related products used at or on the PIVC insertion sites by the participating hospitals are approved by the Brazilian regulatory agencies, routinely purchased by the hospital and available to the physicians and nurses at the time of the study. Characteristics of the products

used at the PIVC insertion sites observed during the study will be documented. All PIVC brands will be observed in the context of this study.

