3.1 Study Type

This will be a national, multicenter, cross-sectional study to assess the prevalence of PIVC-related complications in Brazil. Estimates of the prevalence of clinical and mechanical complications, as well as quality issues associated with PIVC management, will be studied. Moreover, hospital- or ward-specific standards of practice for PIVC management will be described. The study will be considered the pre-study stage of a pre-post interventional study. The de-identified data from this study will be used to calculate the effect of the intervention on the PIVC complication rate.

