3.3 Study Procedures

[figure not shown]

Figure 1– Flowchart of study activities

All of the study team will receive training on the study protocol and other protocol-related procedures prior to study start. At each center, the study will only start after the study protocol and PIVC site assessment training is completed (Figure 1).

Study procedures will be completed in a single center (pilot study site) prior to initiating study activities in the remaining centers. This strategy will allow for the adjustment of any training or monitoring needs identified at the first center. At each study site, including the pilot study site, study activities at the participating wards will be performed in parallel. The Principal Investigator (PI) will be responsible for selecting, at each site:

- The wards that will be audited within the context of this study.
- The healthcare professionals (auditors) that will be responsible for auditing the participating wards. Auditors will be healthcare professionals (e.g. nurse, resident physicians) with extensive experience in PIVC therapy and who are employed by the study site.

Once the PI has selected the hospital's wards that will be participating in the study, the PIVC Therapy Standards of Practice Questionnaire will be completed by him/her or a designee. If there are individual PIVC therapy standards of practice per ward, rather than hospital-wide standards, the PI will interview the ward nurse manager or a ward clinician of the selected wards and complete the PIVC Therapy Standards of Practice Questionnaire for each ward.

To minimize subject selection bias, all subjects will be identified and invited to participate in the study consecutively, as the auditor goes through the ward. An informed consent process will be carried out by the PI, auditor or a designee. After the subject provides his/her written informed consent to participate in the study, data will be collected from the subject's medical records and by observation of the PIVC site. All PIVC sites, regardless of catheter commercial brand, should be assessed. Data on each PIVC site will be recorded on the Individual PIVC Questionnaire.

In addition to collecting general characterization data on the patient and the PIVC, the auditor will be observing the PIVC site for presence of the following complications (see Appendix I for definitions):

- Clinical complications:
 - Phlebitis:
 - According to grade: grade 1-4

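### The exploratory association analyses pool three hospitals and commit to no hospital term, so a factor unrelated to complications within every hospital can appear associated overall

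*Combined protocol and SAP*

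**What the plan says.** Section 6.2.4 sets the aim of "identifying the subject- and PIVC characteristics associated with the occurrence of PIVC-related complications". For single factors it states that "The association of qualitative variables with the occurrence of PIVC-related complications will be performed with the chi-squared test or with the Fisher's test", with Student's t or Mann-Whitney for quantitative factors. No stratification is mentioned. GEE models with a logit link "will be used to identify the most important patient characteristics associated with the multivariate binary occurrence of PIVC-related complications", "considering the correlation structure assumed as exchangeable within patients". Odds ratios with 95% confidence intervals are to be reported at the 5% level.

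Hospital appears in the statistics section's analysis rules only in 6.2.1: "Data will be presented for the overall study sample, as well by hospital and by hospital ward". That governs presentation. It does not say whether associations are shown by hospital, and it adjusts no test or odds ratio.

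Elsewhere the protocol ties factors and assessment to hospital. Products are "routinely purchased by the hospital and available to the physicians and nurses at the time of the study" (1.3). Section 3.1 says that "hospital- or ward-specific standards of practice for PIVC management will be described". Auditors are professionals "with extensive experience in PIVC therapy and who are employed by the study site" (3.3).

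**The concern.** Hospital confounds a pooled association when two things hold together: the factor is used unevenly across hospitals, and complication rates differ across the same hospitals. The protocol makes both plausible. Hospital purchasing can drive dressing, securement and connector type. Local practice, case mix and site-employed auditors can all move the recorded complication rate. Training before start, the pilot site, monitor-triggered retraining and the shared definitions in Appendix I should reduce differences in recording, but they leave real differences in products, practice and patients.

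What is at stake is interpretation. Section 6.2.4 looks for the most important characteristics at a 5% level, and a between-hospital difference could be read there as a property of a dressing, a gauge or a patient group.

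**Working it through.** **Inputs from the documents.** Three hospitals (3.2); at least 100 PIVCs each, 300 in all (6.3); 5% significance level (6.2.1), taken as two-sided. The only plan figure to reproduce is 3 × 100 = 300, which agrees. Section 6.3 states that no formal sample size calculation was made.

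**Assumed inputs.** The documents give no hospital rates and no factor use. Three sets of hospital complication rates are used: A 30/35/40%, B 25/35/45%, C 35/42.5/50%. Set C spans the 35% to 50% failure range in 1.1, borrowed only as a spread, because failure is not point prevalence. Factor use is 20/50/80%, or 35/50/65% as a milder case. Within each hospital the factor has no association with complications (odds ratio 1).

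**Step 1: expected pooled table, use in the same order as the rates.** Expected complications are the sum over hospitals of 100 × use × rate among exposed PIVCs, and of 100 × (1 − use) × rate among unexposed PIVCs.

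- A: exposed 6 + 17.5 + 32 = 55.5 of 150; unexposed 24 + 17.5 + 8 = 49.5 of 150. OR = (55.5 × 100.5)/(94.5 × 49.5) = 1.19.
- B: 5 + 17.5 + 36 = 58.5 of 150 against 20 + 17.5 + 9 = 46.5 of 150. OR = (58.5 × 103.5)/(91.5 × 46.5) = 1.42.
- C: 7 + 21.25 + 40 = 68.25 of 150 against 28 + 21.25 + 10 = 59.25 of 150. OR = (68.25 × 90.75)/(81.75 × 59.25) = 1.28.

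The Mantel-Haenszel odds ratio is 1.00 in all three. Reversing the order of use gives 0.84, 0.70 and 0.78.

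**Step 2: how often the pooled test rejects.** Chi-squared on the expected tables, 300(ad − bc)² divided by the product of the four margins, is 0.53 (A), 2.11 (B) and 1.10 (C). Used as noncentrality parameters on 1 degree of freedom, these give rejection of about 11%, 31% and 18%. Simulation agrees (20,000 runs; per hospital 66 patients with one PIVC and 17 with two; within-patient correlation 0.4; PIVC-level factor):

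| Pooled chi-squared, nominal 5% | A | B | C |
|---|---|---|---|
| Use 20/50/80%, same or reversed order | 12% | 31% | 19% |
| Use 20/50/80%, other four orderings | about 7% | 11-12% | 9% |
| Use 20/50/80%, average of all six orderings | 8.6% | 18.1% | 12.2% |
| Use 35/50/65%, same or reversed order | 6.7% | 11.3% | 8.3% |

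At use 35/50/65% the other orderings give 5.4% to 6.7%. With equal rates, or with equal use, rejection is 4.8% to 5.6%, so both must differ for any inflation to appear.

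**Step 3: the GEE.** With the same PIVC-level factor, use 20/50/80% in the same order and no other covariate, the within-patient exchangeable GEE rejects 10.1%, 24.7% and 15.8% (10,000 runs). Adding hospital brings this to 5.1-5.6%. For a patient-level factor under rates C (600 runs, 80 single-PIVC and 10 two-PIVC patients per hospital, correlation 0.2), it rejects about 18% with OR 1.29 without hospital, and 5.2% with OR 1.00 with hospital.

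**Step 4: stratified alternative.** Hospital-stratified Cochran-Mantel-Haenszel (CMH) tests reject 4.7% to 5.4% for a PIVC-level factor. They reject 6.4% to 6.5% for a patient-level factor, because CMH ignores correlation between PIVCs in one patient.

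**Step 5: precision cost.** The SE ratio is approximately √(total exposure variance ÷ mean within-hospital exposure variance).

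- 20/50/80%: within = (0.16 + 0.25 + 0.16)/3 = 0.19; √(0.25/0.19) = 1.15.
- 35/50/65%: within = (0.2275 + 0.25 + 0.2275)/3 = 0.235; √(0.25/0.235) = 1.03.
- 2/2/98%: within = 0.0196, total = 0.34 × 0.66 = 0.2244. Only 8.7% of the variance is within hospitals, and the SE is about 3.4 times larger.

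**The case against.** A reader might infer that the GEE as planned excludes hospital. The documents do not support that. Section 6.2.4 gives no covariate list, and the quoted phrase describes the working correlation, not the mean model. The plan is silent, and Section 6.5 allows deviations to be described and justified. What remains is that nothing commits the analyst to a hospital term, and a term added after the results are seen is a post-hoc choice.

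A reader might also take the rejection rates as the plan's type I error. They are not. The plan seeks characteristics associated with complications and claims no within-hospital or causal effect. In these scenarios the pooled association is real as a description, so the rates are false positives only against a within-hospital null. That null is the useful one if results are read as being about products or patients, but choosing it is a judgement.

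The GEE sentence speaks of patient characteristics, so on its literal wording a PIVC factor reaches only the unstratified tests. The wording may be loose, since the section's aim covers both kinds. On either reading a gap remains: PIVC factors get no adjustment, or the GEE for any unevenly distributed factor lacks a stated hospital term.

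Section 1.2 expects the study's prevalence data to help sites evaluate and procure products. It does not say that pooled exploratory odds ratios serve that purpose, so the link to product choice is an inference.

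Finally, practice may vary by ward as well as by hospital. A hospital term removes only between-hospital differences. That limit stands.

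**Conclusion.** The point holds as an optional improvement to an exploratory analysis. The single-factor tests are unstratified and the GEE commits to no hospital term, while the protocol's own description links products, practice and auditors to hospital. If rates and factor use both differ by hospital, pooled tests reject about 12% to 31% against a within-hospital null at use 20/50/80% in the same or exactly reversed order, and about 5% to 12% at milder use or in other orderings. These sizes rest entirely on assumed rates, use and within-patient correlation. The gap in the text is certain; its practical importance in this study is not known. The analyses are to be done only if appropriate (6.1.3), and the primary and secondary prevalence estimates do not change.

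**What to change.** In Section 6.2.4:

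- Add hospital as a fixed effect (two parameters) to the GEE models, keep exchangeable correlation within patient, and state that the models cover patient and PIVC characteristics. Clustering robust errors on only three hospitals would be unreliable, so a fixed effect is the workable form.
- Replace the unstratified tests with single-factor GEEs that include hospital, for qualitative and quantitative factors alike.
- Use hospital-stratified CMH only for PIVC-level qualitative factors, and exact stratified tests where cells are sparse, noting that these ignore within-patient correlation.
- Report factors that are nearly uniform within a hospital descriptively, stating that their association cannot be separated from hospital.

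The cost is SAP wording, with no new data. The SE of the log odds ratio rises about 15% at use 20/50/80% and 3% at 35/50/65%. For a nearly hospital-wide factor (2/2/98%), CMH power for a within-hospital odds ratio of 2 (base rate 30%, independent PIVCs) is about 14%, against 82% at equal 50% use. Adjustment cannot rescue such factors, hence the descriptive reporting.
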